4.2 STAGE 2 (Feasibility study of the developed intervention)

This is a prospective cohort study of individuals with an AAA using the intervention developed in Stage 1.

Following development of the cardiovascular-risk reduction intervention for patients with an AAA, we will commence a prospective cohort study in several NHS AAA screening and surveillance centres We will prospectively recruit consecutive individuals with an AAA from NHS sites and ask them to use the intervention over a period of six months.

5 STUDY SETTING

The study will recruit participants from the abdominal aortic aneurysm screening and surveillance programmes for both Stage 1 and Stage 2.

For Stage 1, they will be invited to a number of focus-groups and workshops, alongside experts in cardiovascular health care from England, to create a package which will address cardiovascular risk reduction in men who have an AAA.

For Stage 2, they will be invited to use the purpose-built cardiovascular risk-reduction programme to improve their heart health, taking part in a prospective cohort study.

All research activities will take place in England and the NHS (in existing NHS AAA screening and surveillance programmes).

6 PARTICIPANT ELIGIBILITY CRITERIA

Patients:

Adult men (>18 years of age) who have been identified to have an AAA through participation in the NHS screening programmes will be invited to take part in the relevant study workshops/focusgroups/interviews (for Stage 1) or use the purpose-built cardiovascular risk reduction programme (for Stage 2).

Stakeholders:

As far as expert participants are concerned, any adult stakeholder who is in some way involved in providing care for individuals with an AAA will be invited to take part. The pool of participants will be drawn from online resources of stakeholder groups and societies relevant to the care of individuals

with aneurysms (e.g. the Vascular Society of Great Britain and Ireland, Society for Vascular Nursing, the British Heart Foundation, the Circulation Foundation).

6.1 Inclusion criteria

PATIENTS in either Stage of the study:

Adult men with an abdominal aortic aneurysm (defined as maximal infrarenal aortic diameter above 3.0cm)detected via the existing NHS aneurysm screening programme, who are able to provide written informed consent.

Adult relatives or care givers of men with an abdominal aortic aneurysm, who are also able to provide written informed consent.

EXPERTS & STAKEHOLDERS in either Stage of the study:

Doctors, nurses and healthcare providers with experience in providing care for men with aneurysms, who are also able to provide written informed consent.

6. 2 Exclusion criteria

The following will not be able to take part in the study (either Stage 1 or Stage 2): Individuals who cannot provide written informed consent. Individuals who cannot speak/write in English.

For stage 2 only: patient who are underweight or currently serving a custodial sentence

7 STUDY PROCEDURES

Schedule of procedures (Gantt chart)

After a six-month set-up period, Stage 1 will commence, lasting for nine months and followed by a six-month analysis period used to finalise the intervention and four months to train the nurses in intervention-delivery.

A feasibility study will then commence (Stage 2) to test the fully-developed intervention. Recruitment will last nine months and follow-up another six months. Analysis and dissemination will last six months.

Procedures	Visits (insert visit numbers as appropriate)				
	Screening	Baseline	Treatment Ph	nase	Follow Up 6 months
Invitation	Visit 1				
Informed consent		Visit 2			
Demographics		Visit 2			
Medical history		Visit 2			
Physical examination		Visit 2			
Vital signs		Visit 2			
Concomitant medications		Visit 2			
Quality of life assessment		Visit 2			
AAA size (ultrasound)		Visit 2			
Commencement of cardiovascular-risk intervention		Visit 2			
Nurse assessment		Visit 2	Visit 3	Visit 4	Visit 5
Adverse event assessments		Visit 2	Visit 3	Visit 4	Visit 5
Physician's Withdrawal Checklist					

Schedule of procedures table for Stage 2 (feasibility study)

7.1 Recruitment

Stage 1: At least ten (10) individuals with AAA in surveillance will take part in the service-development workshops (as outlined above). We aim to have at least 45 responses to the scaffolding questionnaire from each stakeholder group (patient groups and expert groups). Further, at least five (5) expert stakeholders involved in the care of patients with an AAA in screening and surveillance programmes will also be asked to take part in focus-groups and interviews, to refine and finalise the cardiovascular-risk reduction intervention.

Stage 2: At least thirty (30) individuals with an AAA in the AAA screening and surveillance programme will be recruited and they will be followed-up over a minimum of six months. This will allow us to assess the primary outcome of interest (feasibility and acceptability). Participants that consent will be interviewed to further explore the feasibility of the intervention.

Further, at least five (5) expert stakeholders will be recruited to take part in interviews to assess the acceptability and fidelity of the intervention delivery by healthcare-staff in the participating NHS AAA screening and surveillance programmes.

7.1.1 Participant identification, screening, and recruitment

Potential participants will be identified by reviewing the list of men in aneurysm surveillance within the local aneurysm screening programmes. This will be overseen by the CI who is a clinician (vascular surgeon) who provides clinical care for patients with aneurysm in Leicestershire and already has access to the Leicestershire aneurysm screening programme lists as an NHS care provider.

Potential participants will then be contacted during their surveillance appointment at the aneurysm screening programme and via mail correspondence. A Participant Information Sheet (PIS) will be given to the potential participants and they will have the chance to ask questions. A minimum period of one day will be given to the potential participants to consider taking part in the study prior to signing a written informed consent formed. Posters and leaflets will also be used at the aneurysm screening programme clinics and vascular imaging departments at NHS hospital sites.

The potential participants will all be under the care of a regional aneurysm screening programme

A list of men who have consented to be contacted about taking part in future research is already available in local aneurysm screening units. This consent for future contact is established at the time of screening for aneurysm in all men who attend for screening. These individuals will then be contacted by the CI and/or the study team and will be given a PIS, either in one of their clinic appointments (secondary care), when they attend their surveillance scan in the screening/surveillance programme (community), via post/email, or via telephone invitation. A minimum of one day (24 hours) will be given to the patients in order to consider their participation after they have received their PIS. They will be allowed as much time as they wish in order to consider taking part and they will be given ample time to discuss their queries regarding the study (in both Stage1 and Stage 2) with the CI and the study team at each study site.

For Stage 1, the potential participants will be asked to fill in the scaffolding questionnaire first and then attend (potentially) the focus groups and/or interviews in the future (once they have signed written informed consent).

For Stage 2, the participants will be given the intervention documents and leaflets which are relevant to their personalised risk factors and they will continue with their standard NHS care outside the CRISP study. Participation in the study will not alter their AAA screening and surveillance scans or attendance to any other NHS service. The intervention is based on existing NICE guidance (best medical and surgical therapy) and NHS principles.

The cardiovascular expert sample will be drawn from the CI and the research team via interrogating the following lists of potential participants: existing national research groups (NIHR and MRC websites), Public Health England (PHE) groups and committees (online lists), NIHR funding panels (online lists), personal contacts of the CI and research team from their clinical environment, NHS AAA screening committees (online lists), Society for Vascular Nursing committees (online lists), the Vascular Society of Great Britain and Ireland (online lists) and the British Heart Foundation (online lists). Potential participants will be invited to take part by the CI via a formal email which will include a letter invitation and an expert PIS. Furthermore, [name] (part of the research team), who is currently chair of the AAA Specialist Interest Research Group (part of the Vascular Society of Great Britain and Ireland), will invite those who sit on this committee to join the research. General Practitioners from primary care in the wider Midlands area will also be approached via email (as above) which will include the formal invitation letter and an expert PIS. Finally, academics with an interest in cardiovascular sciences and public health will be invited in an identical fashion from three institutions: University of Leicester, University of Birmingham, and King's College London.

7.1.2 Payments

Participants will not be paid for taking part in either Stage 1 or Stage 2 of this research. Travel costs will be reimbursed to those attending the qualitative workshops/focus-groups/interviews.

7.2 Consent

Informed consent will be obtained prior to the participant undergoing any activities that are specifically for the purposes of the study.

A discussion will take place between the potential participant or his/her legally acceptable representative and a member of the research team about the nature and objectives of the study and possible risks associated with their participation.

All participants will have the opportunity to ask questions regarding takin part and withdrawing from this research.

A Patient Information Sheet (PIS) which has been approved by a REC will be given to all potential participants.

An assessment of capacity will take place prior to obtaining written informed consent. For consent to be ethical and valid in law, participants must be capable of giving consent for themselves. A capable person has to:

- understand the purpose and nature of the research
- understand what the research involves, its benefits (or lack of benefits), risks and burdens
- understand the alternatives to taking part
- be able to retain the information long enough to make an effective decision.
- be able to make a free choice
- be capable of making this particular decision at the time it needs to be made (though their capacity may fluctuate, and they may be capable of making some decisions but not others depending on their complexity)
- where participants are capable of consenting for themselves but are particularly susceptible to coercion, it is important to explain how their interests will be protected

The participant must personally sign and date the latest approved version of the informed consent form before any study specific procedures are performed.

Written and verbal versions of the participant information and Informed consent will be presented to the participants detailing no less than: the exact nature of the study; the implications and constraints of the protocol; the known side effects and any risks involved in taking part. It will be clearly stated that the participant is free to withdraw from the study at any time for any reason without prejudice to future care, and with no obligation to give the reason for withdrawal.

The participant will be allowed as much time as wished to consider the information, though no less than 24 hours, and the opportunity to question the Investigator, their GP or other independent parties to decide whether they will participate in the study. Written Informed Consent will then be obtained by means of participant dated signature and dated signature of the person who presented and obtained the informed consent. The person who obtained the consent must be suitably qualified and experienced, and have been authorised to do so by the Chief/Principal Investigator as detailed on the Delegation of Authority and Signature log for the study. The original signed form will be retained at the study site within the Investigator Site File (ISF). A copy of the signed Informed Consent will be given to participants and a copy retained in the participant medical notes.

All informed consent processes will follow the HRA guidance available at: http://www.hra.nhs.uk/resources/before-you-apply/consent-and-participation/consent-and-participant-information/

Informed consent will be checked at all visits.

We will allow participants at least 24 hours to consider their participation in the research and ask questions, once a PIS has been given to them. The original written informed consent forms will be kept safely in a study master file at Glenfield Hospital, University Hospitals of Leicester NHS Trust, [name].

7.3 Baseline data

Stage 1: For the focus-groups and intervention development sessions (qualitative research) we will record the age and size of AAA for patients taking part and the profession of expert stakeholders taking part.

Stage 2: For patients taking part in the prospective cohort study we will record their baseline data (anonymised) based on the "Study Assessments" schedule below (7.4).

7.4 Study Assessments for Stage 2

Each participant in Stage 2 (feasibility study) will be assigned an anonymised participant identification study number once signing a consent form. The following are to be recorded at baseline (day of written informed consent). Demographic information (age and sex/gender)

- Medical and surgical history
- Smoking history, including e-cigarettes/vaping
- o Alcohol intake
- o Weight
- o Height
- Blood pressure
- o Full blood count
- Routine biochemistry including lipid profile
- List of medications
- Quality-of-life using the EQ5D5L tool.

7.5 Follow-up assessments for Stage 2

All participants will be followed-up for a minimum of six months. We will record the following information every time they come into contact with the NHS AAA screening and surveillance service and also at six months (final follow-up appointment):

- Medical and surgical history, change since consent
- Change in smoking history, including e-cigarettes/vaping
- Change in alcohol intake
- · How many components of the intervention they have received
- Date(s) of last appointment with the NHS AAA screening and surveillance service(s).

7.6 Qualitative and fidelity assessments for Stage 2

Semi-structured interviews will be conducted with patients receiving the intervention who consent to interview and with all intervention-provider staff. Topic guides will be developed and piloted/refined across the first few interviews. Interview content will explore participants' and providers' experiences of receiving and delivering the intervention, including barriers to engagement or delivery, acceptability and ideas for improving the intervention. Both patient and healthcare professional interviews will stop when data saturation is reached, which maybe before all participants and healthcare professionals have been interviewed.

All intervention sessions will be audio-recorded and the audio files will be scored independently by the intervention design-team and the person who delivered the intervention, using an intervention fidelity (IF) checklist to assess quality of intervention delivery and the presence or absence of intervention components. The checklist will use a Dreyfus competence-rating scale(20). This method has been used successfully to identify areas of good practice and ideas for intervention refinement in several prior projects including three large-scale NIHR-funded trials.

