3.2 Outcomes

The main outcome **Stage 1** of this study is a purpose-built cardiovascular risk reduction intervention for patients with AAA.

The main outcome measure of **Stage 2** is to assess the feasibility of using the purpose-built cardiovascular risk reduction intervention developed in Stage 1 in patients who have an AAA and who are being seen regularly in existing NHS AAA screening and surveillance centres.

Secondary outcome measures of interest for Stage 2 will include:

Proportion of patients agreeing to take part out of all patients invited (intervention recruitment rate); proportion of patients recruited who provide data at the end of the study period (intervention retention rate); all cardiovascular events; mortality; quality of life using the EuroQol-5D (EQ-5D) questionnaire; weight and other relevant anthropometric information including Body Mass Index (BMI); blood-pressure levels; self-reported medication adherence; smoking status (self-reported); uptake of smoking-cessation services; reason for dropout; low-density and high-density lipoprotein levels as well as routine biochemistry.

4 STUDY DESIGN and METHODS

4.1 STAGE 1 (Development of the cardiovascular-risk reduction intervention with patients and experts/stakeholders)

Completed preliminary work

Identification of the intervention objectives with Patient and Public Involvement (PPI) and expert input

Based on NICE guidance(1), Medical Research Council (MRC) complex-intervention guidance, a systematic literature review, and consultation with patients, GPs as well as cardiovascular experts, we have established the five key intervention targets:

- i. Smoking cessation: A clear and easy to follow pathway should be in place, including patientcentred discussion of barriers and referral to existing expert-services.
- ii. Lifestyle modifications: physical activity and diet should be assessed and individuals should (if needed) be supported in setting and achieving specific targets for change.
- iii. Antiplatelet agents: Aspirin 75mg (or Clopidogrel 75mg if Aspirin is contra-indicated) should be offered to all individuals.
- iv. Lipid control: High-intensity statin-therapy should be offered to all individuals regardless of baseline lipid levels

The antiplatelet and statin strategy are supported by NICE (document CG147) and European Society of Cardiology guidance(2, 3).

v. BP-control: A target of 140/90mmHg should be achieved using the NICE CG127 treatmentalgorithm.

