8. SAMPLES

No clinical samples will be obtained as part of this research outside usual NHS care.

9. Recording and reporting of SAEs

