10.2 Statistical analysis plan

Recruitment, retention, measures-completion rates and participant satisfaction scores will be reported using descriptive statistics with 95% confidence intervals. Qualitative data will be transcribed verbatim and analysed. Intervention fidelity scores will be presented as mean scores and ranges for each intervention component and also broken down by facilitator to examine variation between provider staff. During fidelity scoring, examples of good practice will be extracted to use in training intervention providers for the main trial.

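### Six Stage 2 secondary outcomes in 3.2 have no scheduled six-month collection in 7.5 or the schedule table, and self-reported adherence has none at any visit

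*Protocol*

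**What the plan says.** Section 3.2 lists the Stage 2 secondary outcomes. They include "quality of life using the EuroQol-5D (EQ-5D) questionnaire; weight and other relevant anthropometric information including Body Mass Index (BMI); blood-pressure levels; self-reported medication adherence", uptake of smoking-cessation services, and "low-density and high-density lipoprotein levels as well as routine biochemistry".

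Section 7.4 gives the baseline list, recorded on the day of consent: demographics, history, smoking, alcohol, weight, height, blood pressure, full blood count, biochemistry with lipids, a medication list and the five-level EQ-5D.

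Section 7.5 gives the follow-up list, recorded "every time they come into contact with the NHS AAA screening and surveillance service and also at six months (final follow-up appointment"). It has five items: change in medical and surgical history, change in smoking, change in alcohol, number of intervention components received, and dates of the last service appointments.

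The Stage 2 schedule table in Section 7 has a row for "Quality of life assessment", marked at Visit 2 only. Physical examination, vital signs and concomitant medications are also at Visit 2 only. Two rows reach Visit 5 (six months): nurse assessment and adverse events.

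Section 8 states: "No clinical samples will be obtained as part of this research outside usual NHS care". Section 10.2 plans to report "Recruitment, retention, measures-completion rates and participant satisfaction scores" descriptively with 95% confidence intervals.

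**The concern.** The outcome section promises measures that the data-collection sections do not ask anyone to take at the end of follow-up. A site working from 7.5 and the schedule table would have no instruction to repeat the EQ-5D, weigh the participant, take his blood pressure, ask about adherence or look up his lipids at six months.

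Whether men in surveillance will complete such measures after six months is a natural question for a feasibility study, and 10.2 names measures completion as a reported result. Blood pressure and lipids are also two of the five intervention targets set out in 4.1. A questionnaire or measurement not taken at the six-month visit cannot be supplied later by analysis. A separate statistical analysis plan cannot help either, because it can only analyse what the protocol schedules.

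**Working it through.** There is no stated figure to reproduce. The check sets each outcome in 3.2 against the baseline list (7.4), the follow-up list (7.5) and the schedule table. I count 3.2 as 12 outcomes.

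| Outcome in 3.2 | Baseline (7.4, Visit 2) | Six months (7.5, Visit 5) |
|---|---|---|
| EQ-5D | Listed in both | In neither |
| Weight/BMI | Weight and height in 7.4 | In neither |
| Blood pressure | In 7.4; vital signs at Visit 2 | In neither |
| Self-reported adherence | Not listed; medication list only | In neither |
| Smoking-cessation uptake | Not named; smoking history only | Not named; smoking change only |
| LDL/HDL and biochemistry | In 7.4; no schedule row | In neither |
| Smoking status | In 7.4 | In 7.5 |
| Cardiovascular events | Medical history | History change; adverse events |
| Mortality | Not applicable | SAE reporting (9.3) |
| Recruitment rate | From invitations and consents | Not applicable |
| Retention rate | Not applicable | Any 7.5 item supplied at the end |
| Reason for dropout | Not applicable | No item listed |

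**Count.** Six outcomes (the first six rows) have no listed six-month collection: 6 of 12. Reason for dropout also has no listed item, which would make 7 of 12, but it is a process record and not a six-month measurement. Setting aside the three process outcomes (recruitment, retention, reason for dropout) leaves 12 − 3 = 9 patient-level outcomes, of which 6 lack a six-month entry. The other three (cardiovascular events, mortality, smoking status) can be derived from what is collected.

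**Consistency of the sources.** Section 7.5 and the schedule table agree with each other. Quality of life and vital signs have their own rows, marked at baseline only. So this is not one row dropped by accident: two operational sections agree, and both conflict with the outcome list.

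**What can still be reported.** EQ-5D, weight/BMI, blood pressure and lipids/biochemistry have baseline values and baseline completion. Cessation uptake is available at baseline only if it is asked as part of smoking history. Adherence has neither an instrument nor a collection point at any visit. For all six, six-month values, change from baseline and completion at follow-up are not provided for.

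**Retention.** Section 3.2 defines retention as recruited patients who give data at the end of the study period. The 7.5 items are enough to compute it. A man can therefore count as retained without having completed any of the six measures.

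**The case against.** Several points on the other side are sound and limit the claim.

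- **The nurse assessment might include some of this.** It is scheduled at Visits 2 to 5 and its content is not defined, so blood pressure or weight may be taken in practice. This stands. The exact statement is that the measures are not scheduled at six months. A reader might infer that none of the 30 men will have a value, and the document does not establish that.
- **No time point is attached.** Among the 3.2 outcomes only retention is tied to the end of the study, and 10.2 gives no time point for completion rates. This also stands. A reader might infer that the outcomes and their completion rates cannot be reported at all, but baseline reporting is possible for all but adherence, with the reservation above for cessation uptake.
- **The progression decision does not need these data.** Section 10.1 rests it on recruitment, retention and satisfaction. The harm is therefore confined to the secondary outcomes and to measures completion at follow-up.
- **The protocol does not plan to estimate standard deviations for a later trial, and names no outcomes for one.** An argument from those uses would import aims that are not stated. Nor is it right that no change in any risk factor is recorded, since 7.5 records smoking change.
- **Section 8 does not contradict 7.4.** A reader might infer that baseline lipids are ruled out. Recording a routine NHS result fits both sections. What is missing is a time window and a six-month entry.

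None of this removes the mismatch. An undefined nurse assessment is weak ground for assuming a repeat of measures whose own rows stop at Visit 2, and it gives adherence no instrument.

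**Conclusion.** The point holds as an internal contradiction. Section 3.2 names six outcomes for which neither 7.5 nor the schedule table sets a six-month collection point, and self-reported adherence has none at any visit. That is 6 of 12 listed outcomes, or 6 of 9 patient-level ones. The counts depend on how the 3.2 list is divided; the mismatch does not.

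If the protocol is followed as written, and if the nurse assessment adds nothing beyond what 7.5 lists, these outcomes can be described at baseline at most, adherence not at all, and the completion rates in 10.2 cannot cover follow-up for them. The conclusions on recruitment, retention, events, mortality and smoking status stand as planned. It would be wrong to read this as a failure of the study's main feasibility aim.

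**What to change.** Reconcile 3.2, 7.4, 7.5 and the schedule table.

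- Add EQ-5D-5L, weight/BMI, blood pressure, current medications, self-reported adherence and uptake of smoking-cessation services to 7.5 and to Visit 5, or define the nurse assessment so that it contains them.
- Add self-reported adherence to the 7.4 baseline list, with a named instrument.
- For lipids and biochemistry, record the most recent routine NHS result within a stated window at baseline and at six months, and count an absent result as missing in the completion rate. This respects Section 8.
- Remove from 3.2, or relabel as a baseline descriptor, any outcome that will not be collected at six months. This alone would resolve the contradiction for that outcome, but without follow-up information on it.
- State in 10.2 the time point to which measures completion refers.

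The cost is a protocol and CRF amendment and a few extra minutes at a visit that already exists. The protocol gives no visit length. Even at an assumed 10 to 15 minutes per man, 30 men come to 30 × 10 = 300 to 30 × 15 = 450 minutes, or 5 to 7.5 hours of staff time in all. No new samples are needed.
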